2.1 Background and rationale

Maternal undernutrition is a global public health problem with far-reaching effects for both mothers and infants (1). Poor maternal nutrition negatively affects fetal growth and development. Both micro and macro-nutrients are required for the physiological changes and increased metabolic demands during pregnancy, including fetal growth and development. Inadequate intake of vitamins and minerals is known to negatively affect the health, function, and survival of the mother and fetus. Maternal iodine deficiency is associated with delays in neural, intellectual and physical development; folate deficiency is associated with a higher risk of neural tube defects; vitamin A deficiency in mothers can lead to night blindness; iron deficiency anemia is believed to lead to low birthweight and increased perinatal mortality (1).

Women in Bangladesh have poor diets and are struggling to meet their nutrient requirements, especially during pregnancy and lactation when requirements are higher. Women's diets are generally monotonous: rice accounts for as much as 77% of women's energy intake, with oil contributing 7%, vegetables 6%, and fish 3% (2). In a micronutrient survey conducted in 2011/12 in Bangladesh, up to 26% of non-pregnant and non-lactating women were found to be anemic, and a large share suffer from deficiencies in micronutrients such as zinc (57%), iodine (42%), iron (7%), vitamin B12 (6%), and vitamin A (5%) (3). Results from a nationally representative survey of rural Bangladesh conducted by IFPRI in 2011/12 suggested inadequate intake of several nutrients—iron (65% of required intake), zinc (22%), and vitamin A (97%)²—among women of reproductive age, as well as low intakes of energy (47% of women had energy intakes below estimated energy requirements [EER](this draft paper uses data from IFPRI's 2011/12 Bangladesh Integrated Household Survey)(4). Among pregnant women, the National Low Birth Weight Survey (NLBS) 2015 reported a prevalence of anemia of 55% (5). A recent dietary survey of 600 pregnant women from four of Bangladesh's poorest districts also documented low energy intakes (46% < EER and 28% < 85% EER) and alarmingly high probabilities of inadequate micronutrient intakes (94% for iron, 75% for zinc, 77% for vitamin A, 93% for calcium, 87% for folate, and 66% for vitamin B12) (6). The excessively high probabilities of inadequate nutrient intakes found in this sample of pregnant women (compared to those in all women of reproductive age from the national survey) may be due in part to the higher nutrient requirements—and inability to meet them—during pregnancy and to the low socioeconomic status of women in this sample. The large disparities that exist between socioeconomic groups, education levels, and urban and rural areas in Bangladesh are well documented and affect many nutrition and diet indicators and their determinants (3,7,8).

Maternal undernutrition during pregnancy is associated with a range of adverse birth outcomes, including stillbirths, preterm births, low birthweight, and small-for-gestational-age (SGA) neonates (1), all of which remain unacceptably high in Bangladesh (9–11). Estimates from 2010 show that 40% of children born alive in Bangladesh were small for gestational age, 22% had low birthweight, and 14% were premature (12). According to the 2015 NLBS survey, low birthweight affected roughly 22.6% of newborns (5). Maternal nutrition in Bangladesh deserves urgent attention in order to protect the survival, health, and well-being of mothers and their young children.

The Bangladesh National Social Security Strategy (NSSS) called for the development of a national Mother and Child Benefit Program (MCBP) to improve the nutrition and health of women during pregnancy and their children up to age 4. The Ministry of Women and Children Affairs (MOWCA) combined two existing

²The discrepancy between reported iron deficiency from biomarkers and probability of inadequate intake from dietary surveys may be explained by the well-documented high levels of iron present in groundwater (tube well) in the country (3,65). For vitamin A, the discrepancy is likely to be related to seasonal differences, with plant-based vitamin A being present in large concentrations in highly seasonal fruits. Additionally, both dietary surveys were conducted in rural areas, whereas the micronutrient survey (3) was conducted in rural, urban, and urban slum areas.

cash-based safety nets—the rural Maternity Allowance (MA) and urban Lactating Mother Allowance (LMA) programs—to create the MCBP.

The MA program provided 500 BDT (USD 5.95) per month to poor pregnant women to improve access to nutritious food. Benefits started at enrollment (as early as the first trimester of pregnancy) and were provided for 24 months; women were enrolled once a year in July. Starting in the 2018/19 program cycle, key program improvements included better targeting (using widespread promotion of the program and clear and transparent eligibility criteria), monthly enrollment of eligible pregnant women, timely payments every month for 36 months, and a larger cash transfer (800 BDT per month). To help in improving the design of the MCBP, this study tests different packages of interventions (consisting of different combinations of cash transfers, food transfers, and behavior change communication) using a cluster-randomized study design.

Social protection provides a promising platform on which to leverage improvements in nutrition at scale (13). Current evidence specifically on the impacts of social protection on birth outcomes, however, is limited: few studies have been conducted and some of these studies suffer from methodological limitations (14). The study will contribute to filling this knowledge gap. An additional motivation for the study is provided by the recent WHO 2016 Antenatal Care Guidelines (15). The guidelines call for studies on the effectiveness of alternatives to providing energy and protein supplements to pregnant women (which is recommended in undernourished populations). Studying the effectiveness of providing combinations of food and cash will help build this evidence base. A third reason to conduct the study is that both food transfers and cash transfers are commonly used policy instruments in Bangladesh, and the choice of intervention components to scale up in the MCBP will be guided by the findings from this pilot study. The study findings will thus be highly policy relevant.

2.2. Objectives

The study has two specific objectives:

- Assess the impact of adding a food basket targeted at pregnant women to the standard MCBP program package (which provides cash and behavior change communication (BCC)) on a set of outcomes (see Section 6)
- Assess the impact of adding additional cash targeted at pregnant women to the standard MCBP program package (which provides cash and BCC) on a set of outcomes (see Section 6)

Section 3 – Study methods

3.1. Trial design

A three-arm cluster-randomized, non-blinded, community-based, mixed cross-sectional and longitudinal trial is used to estimate the effectiveness of the intervention. The unit of randomization is a grouping of 3 wards³. Each ward group is randomly assigned to one of three study groups, all of which receive the improved maternity allowance program:

- **Arm 1 – “standard” package, i.e., base cash and nutrition behavior change communication (BCC):** pregnant women receive 800 BDT each month and group-based BCC on nutrition with a focus on how to improve their dietary intake during pregnancy.
- **Arm 2 – “standard” package + food basket:** pregnant women in this arm receive the base cash of 800 BDT each month, group-based BCC, and in addition a monthly food basket composed of rice, lentils, and oil valued at approximately 1,000 BDT.
- **Arm 3 – “standard” package + top-up cash:** pregnant women in this arm receive the base cash of 800 BDT each month, group-based BCC, and in addition receive a monthly additional cash transfer of 1,000 BDT instead of the food basket.

The study is a hybrid of a cross-sectional and longitudinal design. It follows women from their second trimester of pregnancy to around 2 months after childbirth. A census is conducted to identify households with women who met the program’s eligibility criteria (see Section 5.2). The study then uses a total of 6 three-month long data collection waves. Women in the 2nd trimester of pregnancy (based on self-reported last menstrual period⁴ and ultrasound reports and antenatal care cards when available) were enrolled in the study in the first four waves (Figure 1). Household and individual data are collected at enrollment. In the wave following enrollment, data are collected on the same women who are now in the 3rd trimester. Third trimester data collection is conducted at around 34 weeks of gestation (± 1 week). Subsequent waves are used to assess newborn weight and length (collected within 72 hours after child birth) and to assess anthropometric and other outcomes at around 2 months postpartum (61 days ± 1 week). In the final follow-up round (1 month in length), women in the 3rd trimester of pregnancy not captured in wave 5 are surveyed. In addition, the newborn survey is conducted. The number of survey rounds is based on the sample size calculations presented below and field reports regarding the actual number of study subjects enrolled and successfully followed up.

³ The administrative structure in Bangladesh consists of divisions (8), districts (64), subdistricts or upazilas (491), and unions. Up to about 15 years ago, each union consisted of 3 wards. Since then, the ward system was changed to 9 wards per union, each identified by a number (i.e., from 1 to 9). The study uses the old definition of wards (i.e., 3 per union) as the unit of randomization.

⁴ Pregnancy trimesters are defined as follows: 1st trimester: 2 to 13 weeks of pregnancy (meaning, weeks since first day of the last menstrual period); 2nd trimester: 14 to 26 weeks of pregnancy; 3rd trimester: 27 weeks of pregnancy until delivery.

[figure not shown]

Figure 1: Study design (note: dates are approximate)

3.2. Randomization

The six study upazilas (**Table 1**) are located in distinct parts of the country and are quite heterogeneous. Stratifying clusters prior to randomization is used to ensure a more balanced distribution of cluster-level covariates between study arms. Each upazila is a stratum. In each stratum, the largest number of ward groups that is a multiple of 3 is randomly selected, resulting in a total of 144 ward groups. Each ward group is then assigned a random number from a uniform [0,1] distribution using Stata. Stratum-specific tertiles are created using this random number and clusters are assigned to the treatment arm that corresponds to their tertile number. Due to the nature of the intervention, trial assignment is not masked.

Table 1: Study upazilas

Division	District	Upazila
Sylhet	Sylhet	Gowainghat
Khulna	Bagherat	Chitalmari
Rajshahi	Rajshahi	Godagari
Rangpur	Rangpur	Gangachara
Barisal	Barisal	Mehendiganj
Mymensingh	Netrakona	Mohanjanj

3.3. Sample size

Sample size requirements were calculated for the primary study outcomes using the Hayes and Bennet's formulas (16,17), using the following parameters: a 0.05 probability of a type I error, power of 0.90, and 48 clusters per treatment arm. Note that the power of 0.90 (higher than what is typically used) is used to minimize the risk of not detecting a program impact by underpowering the study. Adjustments were further made for intra-cluster correlation (since the study is cluster randomized). The outcome-specific intra-cluster correlation (ICC) coefficients are provided below. The estimated size of the eligible population in the 6 study upazilas was used to calculate the coefficient of variation of cluster sizes (equal to 0.424). We further assumed that baseline covariates provide a small amount of explanatory power of the study outcomes (correlation of 0.1).

We did not adjust the sample size for multiplicity (i.e., carrying out many comparisons). Our thinking is provided in Section 4.1.

We first calculated the required sample size for gestational weight gain and then calculated what minimal detectable effects can be observed with this sample for the other primary outcomes. The literature provides very limited guidance on the expected effect of the planned intervention packages on **gestational weight gain**. The interventions, through their intensive BCC and provision of cash or food basket, are most akin to the provision of supplements to increase energy and protein intake during pregnancy. In Ghana, lipid-based nutrient supplement (LNS) provided during pregnancy increased gestational weight gain in the second and third trimester by 10 g per week ($p=0.09$) when compared with the provision of iron-folic acid (IFA) or multiple micronutrient supplements (MMN)(22). In Bangladesh, the effect of LNS (as compared to IFA) on pregnancy weight gain was limited to multiparous women over 25 years of age: an effect of 34 g per week was found ($P=0.001$)(23). The Women's First Trial which conducted in 4 countries (Democratic Republic of the Congo, Guatemala, India, and Pakistan) found that LNS (compared to control) increased gestational weight gain by 22 g per week (own calculations based on reported values; no p values)(24). Finally, a systematic review and meta-analysis of the effect of balanced energy and protein supplementation on gestational weight gain estimated an average effect of 19 g per week (95% CI: -1.81,39.07)(25). The quality of the evidence, however, was assessed as being of very low quality.

Given the limited evidence from the literature, we based the minimum detectable effect on the difference between observed weight gain and weight gain recommended by the Institute of Medicine (26). Recent studies in Bangladesh found that poor women gain only around 60% of the currently recommended weight gain (adjusted for BMI status)(27,28). We powered the study to detect an effect of 25 g per week, which is equivalent to a 9 to 10% increase relative to current weight gain. Using a standard deviation of weekly gestational weight gain of 161g (average of 4 published studies conducted in Bangladesh (27–30)) and an ICC of 0.01, this requires a sample size of 1,152 women per study arm. The ICC of 0.01 corresponds to a design effect of 1.35. We did not find information on the ICC of gestational weight gain in the literature. Using birth outcome studies, we find that Christian et al. used a design effect of 1.2 in Nepal (31) and West et al. a design effect of 1.15 in a study in Bangladesh (32). An ICC of 1.35 thus appears to be a conservative estimate.

A number of adjustments to these calculated numbers were made. We expect 8.3% fetal loss and 2.3% loss to follow-up between the 2nd and 3rd trimester (33). In order to get the required 1,152 pregnant women per study arm (3,456 women total), we need to enroll 1,286 pregnant women in each arm (3,858 total). For the outcomes measured in newborn children, we assumed 1.7% infant death and 5% loss to follow-up (33). We thus assumed a total of 1,076⁵ newborns in each arm (3,227 total). Any additional outcome-specific adjustments to sample sizes are mentioned below.

The detectable differences for the other primary outcomes measured during gestation are as follows:

- **Dietary intake measures** – Using an ICC of 0.05, the sample size calculated for gestational weight gain allows us to observe an effect size of 0.21. We used previously collected data on diet during pregnancy to estimate the ICC (34). The ICCs for energy and protein intake were 0.02

⁵ Due to the need to use integral numbers for the number of observations per cluster, we used 22 observations per cluster in the sample size calculations or $22 \times 48 = 1,056$ observations per arm. Enrollment is targeted to reach the 1,076 per arm which means that the actual observable differences are slightly smaller than what is shown here.

and 0.03 respectively. The ICC for the probability of adequacy of individual micronutrients ranged from 0.00 to 0.27 but was imprecisely estimated for many micronutrients. This might be due to the limited number of clusters (n=18) in the study. The ICC of 0.05 used here is equivalent to a design effect of 2.37.

Using the SD from a recent study in pregnant women in Bangladesh (SD of 831 kcal for energy and 26.8 g for protein) (34), our study is powered to detect effects of 174 kcal for energy and 5.6 g for protein. To assess whether the energy and protein impacts are reasonable in size, we compare them to the size of the food basket that women in one of the study arms receive, to the evidence from the literature, and to the energy and protein requirements during pregnancy. Assuming that the food is distributed equally among all family members (Table 1), we have a potential impact of the food basket on energy intake of 354 kcal per person per day and on protein intake of 11 g per person per day, i.e., approximately double the minimal detectable difference calculated above. A recent systematic review of interventions to increase energy and protein intake during pregnancy identified only 3 studies that looked at dietary intake as an outcome (25). These 3 studies assessed the impact of nutrition education vs no nutrition education (i.e., no supplements or food transfers were provided). The estimated effect from the meta-analysis was 105.6 kcal for energy and 7.0 g for protein. This is smaller than the minimal detectable effect calculated above, but the reviewed interventions did not provide cash or food transfers. The expected impact of the Jibon intervention on dietary intake is thus larger. Finally, the additional energy requirements during pregnancy are 340-350 kcal/d in the second and 452-500 kcal/d in the third trimester (35,36). Additional protein requirements for the second half of pregnancy are estimated at 0.30 g/kg body weight/d or 15.3 g/d for an average body weight of 51 kg (34,37). The minimal detectable effect estimated above is considerably smaller than the additional energy and protein requirement for pregnancy. In sum, the effects we are powered to detect (174 kcal for energy and 5.6 g for protein) are well within the range of the food basket's possible contribution to the diet, evidence from the literature, and the energy and protein requirements during pregnancy.

A recent study in pregnant women in Bangladesh showed that the mean probability of adequacy (MPA) was 0.41 ± 0.11 (34). We are thus able to detect an impact of 2.3 percentage points in MPA or a 5% change.

COVID-19 Scenario

Fieldwork might be disrupted due to a COVID-19 outbreak. As a consequence, not all survey rounds may be completed as planned. We thus calculated the minimal detectable effect for the dietary outcomes if only one- or two-thirds of the planned interviews can be conducted. Dietary data on one-third of the pregnant women (i.e., 384 women per arm) allows us to observe an effect size of 0.28, and effects of 233 kcal for energy, 7.5 g for protein, and 3.1 percentage points for the mean probability of adequacy. With two-thirds of the sample, these values change to 190 kcal for energy, 6.13 g for protein, and 2.5 percentage points for the mean probability of adequacy.

- **Length of gestation:** Using an SD of 18.1 days (38), an ICC of 0.01 and the other parameters as defined above, we find that the study is powered to detect an impact on the length of gestation of 2.77 days.

- **Preterm birth:** Assuming a prevalence of preterm birth of 20% in the comparison arm (38) and using an ICC of 0.01, the study's sample size is powered to detect a difference of 6 percentage points in preterm birth.
- **Prevalence of emotional violence towards the pregnant woman:** Assuming a prevalence of physical violence 40.0% (prevalence estimate from the Transfer Modality Research Initiative project or TMRI) and using an ICC of 0.01, the study's sample size provides the statistical power necessary to detect a reduction of 7 percentage points in the occurrence of physical violence.
- **Prevalence of controlling behaviors towards the pregnant woman:** Assuming a prevalence of physical violence 79.5% (prevalence estimate from the Transfer Modality Research Initiative project or TMRI) and using an ICC of 0.01, the study's sample size provides the statistical power necessary to detect a reduction of 7 percentage points in the occurrence of physical violence.
- **Prevalence of physical violence towards the pregnant woman:** Assuming a prevalence of physical violence of 19.9% (prevalence estimate from the Transfer Modality Research Initiative project or TMRI) and using an ICC of 0.01, the study's sample size provides the statistical power necessary to detect a reduction of 6 percentage points in the occurrence of physical violence.
- **Stress of the pregnant woman:** Using an SD of 15.4 points (TMRI data), an ICC of 0.01 and the other parameters as defined above, we find that the study is powered to detect an impact on stress in women of 0.91 points (scale ranges from 0 to 40).
- **Stress of the husband of the pregnant woman:** Using an SD of 14.9 points (TMRI data), an ICC of 0.01 and the other parameters as defined above, we find that the study is powered to detect an impact on stress in women of 0.90 points (scale ranges from 0 to 40).
- **Maternal-fetal attachment:** Using a SD of 6 (39) and an ICC of 0.001, this sample size allows us to detect an effect of 0.83 for maternal-fetal attachment. This is equivalent to an effect size of 0.14.
- **Household food security:** Setting the prevalence of household food insecurity to 50% (the worst-case scenario in terms of power) and the ICC to 0.05 (equivalent to a design effect of 2.37), we can detect a change in the prevalence of food security of 10 percentage points. When the prevalence of food insecurity is 80%, the detectable difference is 8 to 9 percentage points.
- **Value of total household consumption:** Using an SD of 922 Tk (TMRI data), an ICC of 0.05 and the other parameters as defined above, we find that the study is powered to detect an impact on total per capita household food consumption of 193 Tk. Using an expected household size in the target population of 5 members, the effect we are able to detect is 965 Tk which is comparable to the size of the total transfer (1,000 Tk).
- **Value of household food consumption:** Using an SD of 621 Tk (TMRI data), an ICC of 0.05 and the other parameters as defined above, we find that the study are powered to detect an impact on total per capita household food consumption of 130 Tk. For an average 5-member household, the detectable difference are 650 Tk. We thus need to assume that at least 65% of the transfer are spent on food (top-up cash) or actually consumed by the household (food). This is a reasonable assumption, given that the BCC emphasizes the importance of using the transfers to improve the diet of the pregnant woman. In addition, TMRI households spent 62% of total expenditure on food.

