- **Prevalence of controlling behaviors towards the pregnant woman:** Assuming a prevalence of controlling behaviors of 79.5% (prevalence estimate from the Transfer Modality Research Initiative project or TMRI) and using an ICC of 0.01, the study's sample size provides the statistical power necessary to detect a change of 7 to 8 percentage points in the occurrence of physical violence (7 if the prevalence increases, 8 if the prevalence decreases).
- **Prevalence of physical violence towards the pregnant woman:** Assuming a prevalence of physical violence of 19.9% (prevalence estimate from the Transfer Modality Research Initiative project or TMRI) and using an ICC of 0.01, the study's sample size provides the statistical power necessary to detect a change of 7 percentage points in the occurrence of physical violence (7 both in case the prevalence increases or decreases).
- **Stress of the pregnant woman:** Using an SD of 15.4 points (TMRI data), an ICC of 0.01 and the other parameters as defined above, we find that the study is powered to detect an impact on stress in women of 1.04 points (scale ranges from 0 to 40).
- **Maternal-infant attachment:** Using a SD of 4 (43), an ICC of 0.001, this sample size allows us to detect an effect of 0.65 for maternal-infant attachment (or an effect size of 0.16). Based on previous literature for the effects of behavioral interventions on maternal-infant attachment score, this effect size is appropriate for this outcome with infants under 12 months of age (44).

Notes on birth length and infant weight and length at 2 months (61 days) of age

⁶ Due to the need to use integral numbers for the number of observations per cluster, we used 20 observations per cluster in the sample size calculations or $20 \times 48 = 960$ observations per arm. Enrollment is targeted to reach the 968 per arm which means that the actual observable difference is slightly smaller than what is shown here.

Sample size calculations for these outcomes reveal that the study is not powered to detect meaningful and feasible effects on these outcomes. The findings are summarized below:

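### Section 3.3: the SDs given for stress (15.4 and 14.9) and the detectable effects given beside them (0.91, 0.90 and 1.04 points) cannot both be right

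*SAP*

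**What the plan says.** Section 3.3 of the SAP sizes the trial on gestational weight gain and then lists the effect detectable for each other primary outcome. Stress appears three times.

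- **Women in pregnancy.** Input: "Using an SD of 15.4 points (TMRI data), an ICC of 0.01 and the other parameters as defined above". Result: "we find that the study is powered to detect an impact on stress in women of 0.91 points (scale ranges from 0 to 40").
- **Husbands.** Input: "Using an SD of 14.9 points (TMRI data), an ICC of 0.01 and the other parameters as defined above". Result: "we find that the study is powered to detect an impact on stress in women of 0.90 points (scale ranges from 0 to 40"). The wording refers to women although the entry is for husbands.
- **Women at 2 months postpartum.** The SD and ICC are those for women in pregnancy. Result: "we find that the study is powered to detect an impact on stress in women of 1.04 points (scale ranges from 0 to 40").

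Three neighbouring entries serve as comparators.

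- **Length of gestation**, detectable effect 2.77 days: "Using an SD of 18.1 days (38), an ICC of 0.01 and the other parameters as defined above".
- **Maternal-fetal attachment**, in pregnancy: "Using a SD of 6 (39) and an ICC of 0.001, this sample size allows us to detect an effect of 0.83".
- **Maternal-infant attachment**, at 2 months: "Using a SD of 4 (43), an ICC of 0.001, this sample size allows us to detect an effect of 0.65".

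Section 6.1 reserves primary status for predefined outcomes on which the trial has adequate power for an effect that is both feasible and meaningful.

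**The concern.** With the number of clusters, cluster size, ICC, covariate correlation, alpha and power all fixed, the detectable effect is a constant multiple of the SD. Two outcomes that share those inputs must show the same ratio of effect to SD. Stress in pregnancy and length of gestation share them, and their ratios differ by a factor of about 2.5. Maternal-fetal attachment, with an SD of 6 and a smaller ICC, is given a detectable effect of 0.83, almost the same as the 0.91 given for an SD of 15.4.

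Stress is primary for the woman at three time points and for the husband at two. The entries in section 3.3 are the plan's only support for its power on this outcome. As printed, a reader cannot tell whether the trial detects about 0.9 or about 2.4 points on a 0-40 scale. The two readings lead to different interpretations of a null result.

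**Working it through.** **Inputs (SAP section 3.3, except sidedness from 4.1).** Two-sided alpha 0.05; power 0.90; k = 48 clusters per arm; CV of cluster size 0.424; covariate correlation r = 0.1. In pregnancy there are 1,152 women per arm, so m = 1,152/48 = 24 per cluster (derived, not printed). At 2 months m = 17 (816 per arm). The ICC for stress is 0.01.

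**Formulas.**

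- Design effect: DE = 1 + ((CV² + 1)m − 1) × ICC
- Detectable effect: MDE = (t₀.₉₇₅ + t₀.₉₀) × SD × √(2 × DE × (1 − r²)/(48m)), with 94 df, so the two quantiles sum to 1.986 + 1.291 = 3.276

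**Step 1: reproduce the plan's other entries that state an ICC.**

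| Outcome | SD | ICC | m | Computed | Stated |
|---|---|---|---|---|---|
| Energy (kcal) | 831 | 0.05 | 24 | 173.6 | 174 |
| Protein (g) | 26.8 | 0.05 | 24 | 5.60 | 5.6 |
| Length of gestation (days) | 18.1 | 0.01 | 24 | 2.774 | 2.77 |
| Total consumption (Tk) | 922 | 0.05 | 24 | 192.6 | 193 |
| Food consumption (Tk) | 621 | 0.05 | 24 | 129.7 | 130 |
| Maternal-fetal attachment | 6 | 0.001 | 24 | 0.826 | 0.83 |
| Maternal-infant attachment | 4 | 0.001 | 17 | 0.652 | 0.65 |

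The formula also returns the plan's design effect of 2.37 for an ICC of 0.05. It therefore behaves as the plan's own.

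**Step 2: apply it to stress.** DE is 1.273 at m = 24 and 1.191 at m = 17. The detectable effect is 0.153 SD in pregnancy and 0.176 SD at 2 months.

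| Entry | Printed SD | Computed MDE | Stated MDE | Computed/stated | Stated MDE in SD units | SD implied by stated MDE |
|---|---|---|---|---|---|---|
| Women, pregnancy | 15.4 | 2.36 | 0.91 | 2.59 | 0.059 | 5.94 |
| Husbands | 14.9 | 2.28 | 0.90 | 2.54 | 0.060 | 5.87 |
| Women, 2 months | 15.4 | 2.71 | 1.04 | 2.61 | 0.068 | 5.91 |

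If the printed SDs are right, power at the stated effects (noncentral t, 94 df) is about 0.24, 0.25 and 0.24.

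**Step 3: the same result without a formula.** Gestation gives 2.77/18.1 = 0.153. Then 0.153 × 15.4 = 2.36 and 0.153 × 14.9 = 2.28. At 2 months, maternal-infant attachment gives 0.65/4 = 0.1625 with an ICC ten times smaller than that for stress. Stress cannot do better than this, so an SD of 15.4 gives at least 0.1625 × 15.4 = 2.50 points, against 1.04 stated.

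**Step 4: could another input explain the gap?**

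- An ICC of 0 still gives 2.09, 2.02 and 2.49.
- The printed design effect of 1.35 for an ICC of 0.01 gives 2.43 and 2.35 in pregnancy, which widens the gap.
- Reaching 0.91 with an SD of 15.4 needs a covariate correlation of about 0.92, against the stated 0.1.
- Reading 15.4 and 14.9 as variances overshoots the other way, to about 0.60, 0.59 and 0.68 (normal quantiles).
- The effects are not the SDs times one constant. Allowing for rounding, 0.91/0.90 is at most 0.915/0.895 = 1.022, while 15.4/14.9 is at least 15.35/14.95 = 1.027.

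**Step 5: a related slip in the same section.** The notes on birth length and infant length print SDs of 2.12 mm and 2.02 mm beside detectable effects of 3.5 mm and 3.6 mm. Assuming an ICC of 0.01 (none is stated there), those SDs give 0.35 mm and 0.36 mm. Read as cm they give 3.49 mm and 3.56 mm.

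**The case against.** The mismatch itself is hard to dispute; the argument is about its weight. The sample size rests on gestational weight gain, so nothing in the design changes. The three stated effects agree with one another, all implying an SD near 5.9 at both cluster sizes. That suggests a sound calculation beside wrongly entered SDs, which would make the correction editorial. In SD units the detectable effect is 0.153 or 0.176 whichever SD is right, close to what the plan accepts for other primary outcomes (gestation 0.153, attachment 0.14 and 0.16, diet 0.21). Section 3.3 offers no benchmark for a meaningful change in stress, so the section 6.1 criterion could not be fully checked even with consistent figures. The TMRI score may also have been on a different scale.

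Most of this stands, and it limits the finding. The power of about 0.24 to 0.25 is conditional on the printed SDs and is not evidence of underpowering. The slip in the length SDs is only an analogy. The largest possible SD on a 0-40 scale is 20, so 15.4 and 14.9 are not excluded. None of this removes the contradiction. Whether an effect is meaningful has to be judged in points, and the points are what the document leaves open. A scale mismatch would be one more reason to look up the SD.

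**Conclusion.** The point holds. Under the plan's own parameters the printed stress SDs give 2.36, 2.28 and 2.71 points, not 0.91, 0.90 and 1.04. The conclusion rests on 24 women per cluster in pregnancy (1,152/48) and on a standard cluster formula that reproduces the plan's other entries; the gestation ratio shows the same conflict in pregnancy without that formula.

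The document does not settle which side is wrong. The common implied SD of about 5.9 makes a mis-entered SD the likelier cause, but that is inference. This does not show that the trial is underpowered for stress, and the sample size is untouched. It should be fixed because a primary outcome's stated power cannot be relied on as written.

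**What to change.** Look up the SD of the stress score in the TMRI data for women and for husbands separately, and confirm that it refers to the 0-40 scoring.

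- If it is about 5.9, replace 15.4 and 14.9 and keep the detectable effects.
- If 15.4 and 14.9 are right, restate the detectable effects as about 2.4 points (women, pregnancy), 2.3 (husbands) and 2.7 (women, 2 months).
- If it is some other value, recompute as 0.153 × SD in pregnancy and 0.176 × SD at 2 months.

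In each case add a sentence on whether the effect is feasible and meaningful under section 6.1. No result of this check by itself requires moving stress to the secondary outcomes. In the same edit, correct the husband entry so that it refers to husbands, and check the mm units of the two length SDs.

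The cost is one look-up in existing data and a wording correction in section 3.3. The sample size, model and outcome hierarchy do not change.
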